Secondary Objectives	
To further assess the anti-tumor activity of BGJ398 in patients with GBM and/or other glioma subtypes with FGFR1-TACC1, FGFR3-TACC3 fusion and/or activating mutation in FGFR1,2or 3 based on ORR
 
To further assess the anti-tumor activity of BGJ398 in patients with GBM and/or other glioma subtypes with FGFR1-TACC1, FGFR3-TACC3 fusion and/or activating mutation in FGFR1,2or 3 based on OS
 
To characterize the safety and tolerability of BGJ398

Primary endpoints	PFS rate at 6 months as defined by RANO criteria as assessed by the investigator

Secondary Endpoints
	
ORR (patients with measurable disease) as defined by RANO criteria (Appendix 3) as assessed by the investigator
 
Overall survival (OS)
 
Safety: type, frequency, and severity of AEs and SAEs
 
Tolerability: dose interruptions, reductions and dose intensity, and evaluations of laboratory values

Study design
	
This is an open-label non-randomized, multicenter, phase II study of BGJ398 administered to patients with recurrent GBM and/or other glioma subtypes, whose tumors demonstrate FGFR1-TACC1, FGFR3-TACC3 fusion and/or activating mutation in FGFR1, 2 or 3. . Patients will be enrolled in two groups. Group 1 will enroll patients who are not candidates for surgery. Patients in group 1 will receive BGJ398 on a three week on, one week off schedule. Group 2 will enroll patients who are surgical candidates. Patients in group 2 will receive BGJ398 for 5-10 days prior to surgery and will continue to receive BGJ398 on a three week on, one week off schedule, at a minimum of 2 weeks and no more than 6 weeks following surgery. [REDACTED] Patients from both groups will be evaluated for tumor response and progression by Gd-enhanced MRI every 8 weeks until disease progression or discontinuation from study using RANO criteria.

Population
	
34 adult patients with histologically confirmed recurrent GBM and/or other glioma subtypes with FGFR1-TACC1, FGFR3-TACC3 fusion and/or activating mutation in FGFR1,2 or 3.

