Besides GBM, which features the highest grade of malignancy among glioma (grade IV), lower grade glioma which include grade II and grade III are a heterogeneous group of tumors in which specific molecular features are associated with divergent clinical outcome.

FGFR-TACC fusion

Recently Singh et al. (Singh et al, 2012) reported that a small subset of GBMs (3.1%) harbors oncogenic chromosomal translocations that fuse in-frame the tyrosine kinase coding domains of fibroblast growth factor receptor (FGFR) genes (FGFR1 or FGFR3) to the transforming acidic coiled-coil (TACC) coding domains of TACC1 or TACC3, respectively.

Lentivectors expressing FGFR-TACC fusions injected directly into short term astrocytic cell cultures as well as the brain parenchyma of mice have been shown to fully recapitulate GBM. Subsequently FGFR-TACC induced GBM (and derived cell lines) were successfully treated with FGFR inhibitors such as BGJ398, abolishing the malignant phenotype. Subsequently FGFR3-TACC3 fusions have been identified in pediatric and adult gliomas (Zhang et al, 2013). Recent data shows that FGFR amplification is a poor surrogate for fusion presence and that patients identified with FGFR-TACC fusions in GBM and other gliomas shows radiological evidence of response when treated with FGFR inhibitors (Di Stefano et al, 2015). In conclusion, FGFR-TACC fusions could potentially identify a subset of patients with GBM and/or other glioma subtypes who would benefit from targeted FGFR kinase inhibition.

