4.1 Description of study design

This is a multi-center, open label, phase II study, with 2 groups of patients. BGJ398 will be administered once daily as an oral single agent in 28-day cycles, on a “3 weeks on, one week off schedule.” The study will enroll patients with recurrent GBM and/or other glioma subtypes, whose tumors harbor FGFR1-TACC1, FGFR3-TACC3 fusion and/or activating mutation in FGFR1, FGFR2 or FGFR3 gene.

Group 1 will target patients with RANO tumor progression not eligible for surgical resection. As the primary endpoint is the 6 month progression-free survival rate. Additionally, patients who recently underwent resection and are post-operative without RANO tumor progression may also be eligible for group 1 assuming all inclusion/exclusion criteria are met and most recent surgery has occurred within six weeks of planned first treatment dose.

[figure not shown]
Group 2 will target patients who will have cytoreductive surgery for recurrent disease as part of their routine care. Patients enrolled to group 2 will receive BGJ398 for 5 to 10 days prior to resection.

Following recovery from surgery (a minimum of 2 weeks and no more than six weeks post operatively unless agreed otherwise between Novartis and the Investigator, on a case by case basis), these patients will receive BGJ398 in 28-day cycles, as for patients in group 1. If a patient assigned to group 2 does not undergo planned surgical resection, then the patient will be allowed to continue therapy as per group 1. If a patient enrolled to group 2 needs to undergo surgical resection sooner than initially planned (and having had less than 5 days of BGJ398), then the patient will still be allowed to continue therapy post-surgically as per group 2 regardless of the number of days the patient received BGJ398 pre-surgically.

A total of 34 patients will be enrolled, and it is expected that the ratio of patients in group 1 and group 2 will be approximately 2:1, based on previous GBM trials (Stupp et al 2006, Wong et al 1999; Lamborn et al 2008; Wong et al 2011; Hofer et al 2011; Wen et al 2009; Norden et al 2008; Yung et al 2000). Please see Section 10: Statistical Methods and Data for details.

In order to assess the antitumor activity of BGJ398, patients will be evaluated for tumor response and progression by Gd-enhanced MRI every 8 weeks until disease progression or discontinuation from study using RANO criteria.

Figure 4-1 Study design

Molecular pre-screening

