7.1.4.2 Replacement policy

No replacement will be needed.

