10.1.2 Safety Set

The Safety Set includes all patients who received at least one dose of BGJ398 and have at least one valid post-baseline safety assessment. Patients with FGFR1, 2, 3 and 4 amplifications enrolled prior to protocol amendment 2 will be included in the safety set. These patients will be included in the FAS and their data will be listed and summarized as described below, however they will not be part of the per-protocol set which will be used for the primary analysis.

The statement that a patient had no AE (on the AE eCRF) constitutes a valid safety assessment.

Patients will be classified according to treatment received, where treatment received is defined as:

- The treatment assigned if it was received at least once, or
- The first treatment received when starting therapy with study treatment if the assigned treatment was never received.

[figure not shown]

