10.1.3 Per-Protocol Set

The Per-Protocol Set (PPS) will consist of a subset of patients in the FAS (with FGFR1-TACC1, FGFR3-TACC3 and/or activating mutations in FGFR1, 2 or 3) who are compliant with requirements of the Clinical Study Protocol (CSP). The PPS will include patients who have an adequate tumor assessment at baseline, a follow-up tumor assessment >8 weeks after starting treatment unless disease progression is observed before that time, and no major protocol deviations.

All major protocol deviations leading to exclusion from the PPS will be detailed in the Reporting and Analysis Plan (RAP).

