10.4 Primary objective

10.4.1 Variable

Preliminary tumor activity will be assessed using RANO criteria ([Appendix 3](#)).

Six month progression free-survival (PFS6) rate will be the primary efficacy variable.

For patients in group 1 (non-surgical), PFS is defined as the number of days from the first day of treatment to the date of the first documented disease progression or date of death, whichever occurs first.

For patients in group 2, who undergo surgery, PFS is defined as the number of days from the first day of treatment after surgery to the date of the first documented disease progression or date of death, whichever occurs first.

For patients in group 2, who do not undergo surgery, PFS is defined as the number of days from first day of treatment to the first documented disease progression or date of death, whichever occurs first.

Patients in group 2, who undergo surgery but do not receive at least one post-surgical dose of BGJ398 (i.e., C1D1) will be excluded from the primary efficacy analysis; their data will be listed.

[figure not shown]
The Primary Analysis will be performed on the PPS (24 patients) and the FAS summary will be provided as a supportive analysis (34 patients). The labs, safety, [REDACTED] etc, data for the patient with amplifications using the FAS will be summarized, but the efficacy focus will be on the PPS.

Patients who discontinue the study and are lost to follow-up without a known date of progression or death due to any cause on or before the cut-off date will be censored in the primary analysis at the date of their last available tumor assessment.

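### The protocol summary and SAP 1.1 call all 34 patients fusion- or mutation-positive, but protocol Section 10 makes 34 the FAS with amplified patients and 24 the primary set; SAP Section 3 still sizes on 34, and the rules conflict for a patient with both alterations

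*Protocol*

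**What the plan says.** **Size.** The Population row of the protocol summary plans "34 adult patients with histologically confirmed recurrent GBM and/or other glioma subtypes with FGFR1-TACC1, FGFR3-TACC3 fusion and/or activating mutation in FGFR1,2 or 3". SAP 1.1 repeats that number and molecular description. Protocol 4.1 fixes enrolment: "A total of 34 patients will be enrolled". Section 7.1.4.2 adds: "No replacement will be needed".

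Section 10 uses the same 34 differently. On the earlier amplified patients, 10.1.2 says: "Patients with FGFR1, 2, 3 and 4 amplifications enrolled prior to protocol amendment 2 will be included in the safety set". It also puts them in the FAS. Section 10.4.1 then gives both set sizes: "The Primary Analysis will be performed on the PPS (24 patients) and the FAS summary will be provided as a supportive analysis (34 patients".

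**Operating characteristics.** Protocol 10.8 (Table 10-2) is built on 24 evaluable PPS patients and gives 86.1% success at a true PFS6 of 50%. SAP Section 3 (Table 3-1) is built on 34 patients and gives about 92%. SAP 2.5.2 nevertheless runs the primary analysis on the PPS.

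**Membership.** Of the earlier amplified patients, 10.1.2 says: "however they will not be part of the per-protocol set which will be used for the primary analysis". Section 10.1.3 defines the PPS as "a subset of patients in the FAS (with FGFR1-TACC1, FGFR3-TACC3 and/or activating mutations in FGFR1, 2 or 3", and adds conditions on compliance, baseline scan and follow-up scan. SAP 2.2 repeats that molecular condition and does not carry over the amplification sentence.

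**The concern.** The same 34 patients cannot all be fusion- or mutation-positive and also include patients enrolled on amplification alone. A reader of the summary or SAP 1.1 would expect up to 34 target-population patients in the primary analysis. A reader of Section 10 would expect 24. The difference reaches the stated chance of success, because the SAP quotes it for a set larger than the one it analyses.

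The membership rules raise a second problem. Section 1.1 says that "FGFR amplification is a poor surrogate for fusion presence". That makes amplification a weak indicator of fusion, but it does not make the two mutually exclusive. If an earlier patient has both, the documents do not settle whether that patient counts toward the primary result. In an open-label, single-arm trial, that should be fixed before outcomes can influence the choice.

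**Working it through.** **1. Set sizes.** Among the 34 treated patients, let
- A = amplification with no fusion or activating mutation;
- B = both alterations, enrolled before Amendment 2, and otherwise meeting the PPS conditions;
- E = fusion- or mutation-positive but not compliant or not evaluable.

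Then:
- PPS under 10.1.2 = 34 − A − B − E
- PPS under 10.1.3 and SAP 2.2 = 34 − A − E
- Difference between the rules = B
- Fusion- or mutation-positive group = 34 − A

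The planned gap is 34 − 24 = 10, and 24/34 = 70.6%. With no replacement, exactly 24 results only if A + B + E = 10 (10.1.2) or A + E = 10 (10.1.3). The documents give none of A, B or E. The Population row is true only if A = 0. If at least one amplification-only patient was enrolled and the PPS reaches 24, the positive group numbers between 24 (A = 10) and 33 (A = 1). B lies between 0 and 10. One patient is 1/24 = 4.2% of the planned primary set.

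**2. Reproducing the stated probabilities.** Inputs from protocol 10.4.2, 10.7 and 10.8: Weibull PFS, log scale parameter normal (0, 2.236), shape parameter exponential with rate 1, one patient per month, and the stated interim and final rules. Assumptions: exponential true PFS, time in months, 1,500 simulated trials per scenario. For SAP Table 3-1 an interim at 17 patients was assumed, the number in the protocol summary, because the SAP does not state one.

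Prior check: P(PFS6 < 16%) = 0.649 against the stated 65%; P(PFS6 > 40%) = 0.257 against the stated 25%.

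| Design | True PFS6 | Success, stated | Success, simulated |
|---|---|---|---|
| Protocol: 24, interim at 10 | 25% | 0.026 | 0.025 |
| | 40% | 0.465 | 0.470 |
| | 50% | 0.861 | 0.855 |
| SAP: 34, interim at 17 (assumed) | 25% | 0.003 | 0.008 |
| | 40% | 0.488 | 0.459 |
| | 50% | 0.917 | 0.919 |

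The simulation standard error at 0.855 is √(0.855 × 0.145 / 1500) = 0.009. Each document's table is broadly reproduced on its own sample size, so the two tables describe two different designs.

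**3. Separating size from interim timing at a true PFS6 of 50%.**
- 24 patients, interim at 10: 0.855
- 34 patients, interim at 10: 0.895, so size adds 0.895 − 0.855 = 0.040
- 34 patients, interim at 17: 0.919, so timing adds 0.919 − 0.895 = 0.024

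The stated gap is 0.917 − 0.861 = 0.056. More than half of the simulated gap (0.040 of 0.064) comes from the number of patients, although the split is approximate given the simulation error.

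**The case against.** The strongest reply is that the protocol's own sizing is clear. Table 10-2 is labelled as 24 evaluable PPS patients, and the Population row merely omits the earlier amplified patients. The sentence in 10.1.2 is an aside under the Safety Set. It follows an amendment that dropped amplification as an entry route, so it plausibly means patients enrolled on amplification alone. The working definition is in 10.1.3, which SAP 2.2 repeats. No document reports a patient with both alterations.

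Much of this stands, and it keeps the membership point small. It does not explain why the SAP quotes success on 34 patients for an analysis of the PPS, and the 10.1.2 sentence as written has no exception.

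Four stronger readings are tempting and should not be drawn:
- *That Section 10 makes the fusion- or mutation-positive group 24.* The 24 is that group after the compliance and evaluability conditions; the group itself may be larger.
- *That the protocol expressly excludes fusion-positive amplified patients.* This is inferred from an unqualified sentence; it is not written.
- *That the same tumor enrolled after Amendment 2 would clearly be in the PPS.* This is arguable. The amendment rationale says amplified patients were to be excluded, but Section 5.3 lists no such exclusion.
- *That recruitment might stop at 24 target patients, a ten-month difference.* Protocol 4.1 fixes enrolment at 34, and nothing sets a stop at 24 target patients.

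**Conclusion.** The point holds as two inconsistencies in the current text. First, the summary and SAP 1.1 describe a population of 34 that Section 10 contradicts, and SAP Section 3 carries the mismatch into the operating characteristics. At a true PFS6 of 50% it states about 92% where the protocol states 86.1%. At 25% it states a success probability of 0.003 where the protocol states 0.026. The SAP table is therefore the more favourable one on both counts.

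Second, two rules for the primary set disagree on a patient with both alterations. The effect is 4.2% of the planned set per patient, for a number of patients that is unknown and possibly zero.

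Neither inconsistency invalidates the primary analysis, but both should be resolved before it is run. The first conclusion rests on the documents' own figures; the simulation only confirms that each table fits its own sample size. The second assumes only that amplification and fusion can coexist, which the documents do not rule out.

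**What to change.** 1. In the protocol summary, protocol 4.1 and SAP 1.1, state: *about 34 treated patients (FAS), including those enrolled for amplification before Amendment 2, of whom 24 evaluable with a fusion or activating mutation are expected in the PPS.* Give the number of amplified patients.

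2. In SAP Section 3, replace the 34-patient operating characteristics with those for the 24-patient PPS. Before copying Table 10-2, correct its average sample size of 31.998 at PFS6 40%. That value exceeds 24, whereas 24 − 14 × 0.143 = 21.998. SAP Section 4 says no interim was performed, so also say whether the figures include one. Without it, success at 50% lies between 0.861 and 0.861 + 0.039 = 0.900.

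3. In 10.1.2, limit the exclusion to amplified patients without a documented FGFR1-TACC1 or FGFR3-TACC3 fusion or activating FGFR1-3 mutation, to agree with 10.1.3 and SAP 2.2. Use molecular results documented without regard to outcome and before the primary analysis.

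The cost is wording, with no added patients; FGFR status, including amplification, is already summarised under SAP 2.3. There are two downsides. An amplified patient never tested for a fusion or mutation stays out of the PPS, so membership partly follows testing practice. The SAP's stated chance of success falls from about 92% to about 86%.

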1.1 Overview of disease pathogenesis, epidemiology and current treatment

Glioblastoma (GBM) is a highly malignant brain tumor of astrocytic origin which accounts for over 50% of all gliomas. GBM has an annual incidence rate of 3 to 4 cases per 100,000 people resulting in 240,000 newly diagnosed cases worldwide each year (CBTRUS 2012; Ferlay et al, 2008).

The current standard treatment for GBM is surgical resection followed by radiotherapy with concurrent and adjuvant temozolomide (TMZ). For newly diagnosed GBM, the addition of TMZ to surgery and radiation therapy prolongs median survival (from 12.1 to 14.6 months) and increases the five-year survival rate (from 2% to 10%; hazard ratio 0.63; 95% CI 0.53-0.75; $p < 0.0001$) (Stupp et al, 2009).

However, at recurrence, no cytotoxic or targeted therapeutic has improved the 6-month-PFS rate of 10-20%, a median overall survival of 6-9 months, and an average 5 year overall survival of 3.3% (Stupp et al, 2006; Wong et al, 1999; Lamborn et al, 2008; Wong et al, 2011; Hofer et al, 2011; Wen et al, 2009; Norden et al, 2008; Yung et al, 2000) with the possible exception of bevacizumab.

Bevacizumab, a monoclonal antibody against vascular endothelial growth factor (VEGF), was approved in the US for the treatment of recurrent GBM based on a clinically meaningful and durable objective tumor response rate (ORR 28%-38%, median duration of response 4.2 months). The 6-month-PFS rate in the multiple studies ranged from approximately 29% to 50% and represented a significant improvement over the historical 10-20% 6-month-PFS rate. Despite the improvement in response provided by bevacizumab, most patients with GBM experience relapse within months (Friedman et al, 2009; Kreisl et al, 2009) and options for salvage remain extremely limited.

Genetically, GBM is characterized by complex chromosomal abnormalities and extensive intratumor cytogenetic and histological heterogeneity displaying the genetic alterations that govern the processes of cellular proliferation, survival, invasion and angiogenesis (TCGA 2008; Harada et al, 2000; Walker et al, 2001). Common mutations found in GBM include: EGFR overexpression (70%) (Maher et al, 2006); TP53, RB, INK4a, PDGF-R, VEGF-R, C-Met and HGF and PTEN (Mao et al, 2012).

Besides GBM, which features the highest grade of malignancy among glioma (grade IV), lower grade glioma which include grade II and grade III are a heterogeneous group of tumors in which specific molecular features are associated with divergent clinical outcome.

FGFR-TACC fusion

Recently Singh et al. (Singh et al, 2012) reported that a small subset of GBMs (3.1%) harbors oncogenic chromosomal translocations that fuse in-frame the tyrosine kinase coding domains of fibroblast growth factor receptor (FGFR) genes (FGFR1 or FGFR3) to the transforming acidic coiled-coil (TACC) coding domains of TACC1 or TACC3, respectively.

Lentivectors expressing FGFR-TACC fusions injected directly into short term astrocytic cell cultures as well as the brain parenchyma of mice have been shown to fully recapitulate GBM. Subsequently FGFR-TACC induced GBM (and derived cell lines) were successfully treated with FGFR inhibitors such as BGJ398, abolishing the malignant phenotype. Subsequently FGFR3-TACC3 fusions have been identified in pediatric and adult gliomas (Zhang et al, 2013). Recent data shows that FGFR amplification is a poor surrogate for fusion presence and that patients identified with FGFR-TACC fusions in GBM and other gliomas shows radiological evidence of response when treated with FGFR inhibitors (Di Stefano et al, 2015). In conclusion, FGFR-TACC fusions could potentially identify a subset of patients with GBM and/or other glioma subtypes who would benefit from targeted FGFR kinase inhibition.

1.2 Introduction to investigational treatment(s) and other study treatment(s)

1.2.1 Overview of BGJ398

BGJ398 is an orally bio-available, selective and ATP competitive pan-fibroblast growth factor receptor (FGFR) kinase inhibitor which has demonstrated anti-tumor activity in preclinical, *in vitro* and *in-vivo* tumor models harboring FGFR genetic alterations. BGJ398 belongs to the pyrimidinyl aryl urea chemical class and its chemical name is 3-(2,6-Dichloro-3,5-dimethoxyphenyl)-1-{6-[4-(4-ethyl-1-piperazin-1-yl)phenylamino]-pyrimidinyl-4-yl}-1-methylurea phosphate(1:1).

Please refer to the [Investigator's Brochure] for additional information on BGJ398.

1.2.1.1 Non-clinical experience

At the cellular level, BGJ398 selectively inhibits the kinase activity of FGFR1, FGFR2, FGFR3, and FGFR4 as measured by inhibition of receptor autophosphorylation with IC50 values of 3 - 7 nM for FGFR1, FGFR2 and FGFR3, and 168 nM for FGFR4. In cellular kinase selectivity assays using a panel of BaF3 cell lines rendered IL-3 independent by various tyrosine kinases, the most potently inhibited kinase, in addition to the FGFRs were VEGFR2 and FLT1 with IC50s of 1510 nM and 1591 nM, respectively.

Consistent with inhibition of FGFR autophosphorylation, BGJ398 inhibits FGFR downstream signaling and proliferation of human cancer cell lines harboring genetic alterations of the FGFRs. These include, among others, lung and breast cancer cell lines with FGFR1 gene amplification, gastric cancer with FGFR2 gene amplification, endometrial cancer with FGFR2 mutations and bladder cancer with FGFR3 mutations or FGFR3 translocations (Wesche et al, 2011). In line with its cellular activity, BGJ398 shows anti-tumor activity in multiple models bearing FGFR genetic alterations (Guagnano et al, 2012; Konecny et al, 2013).

